VII- References		References by reference manager		
Evidence based committee (Reviewers)				
1. [name]		Signature		Date
2.				25-V-18
Research plan committee				
1. [name]		Signature		Date
2.				25-V-18

I. Administritive information:

1. Title:

Salivary and serum leptin levels in oral lichen planus patients : A Case-Control study.

-Research question :

Do levels of salivary and serum leptin differ between oral lichen planus patients and healthy control subjects ?

(Primary outcome is serum leptin levels)

2. Protocol registration:

The study protocol; will be registered on www.clinicaltrials.gov upon approval by the ethics committee of Faculty of Dentistry, Cairo University.

3. Protocol version:

18 July 2023, protocol number: 1

4. Funding:

Self-funding

5. Roles and responsibilities:

Investigator: [name], B.D.S 2015 Misr university for science and technology.

The principal investigator, responsible for funding and undergoing the clinical and theoretical work of the trial, collecting data, clarification and conclusions.

[name], Professor of Oral medicine and Periodontology Department, Faculty of Dentistry, Cairo University.

Role: Main supervisor

Responsibilities: initiated the study design. She will afford guidance through the clinical work, revising the theoretical part and help with the conclusions and completion of the data.

[name] [name], Professor of Medical Biochemistry and Molecular Biology, Faculty of Medicine, Cairo University.

Role: co-supervisor

Responsibilities: Assessment of leptin expression profiles in saliva and serum and interpretation of the data.

II. Introduction:

6a. Scientific background

One of the most prevalent muco-cutaneous chronic autoimmune illnesses is oral lichen planus. It has an unknown cause, however factors like systemic illness, psychological illness, dental work, and medication can increase your risk.

Leptin is a hormone that helps with weight loss and also has a role in the body's response to fasting. Leptin's effects on the immunological system, the neuroendocrine system, and development are all worth noting. Infections, endotoxins, and cytokines including tumour necrosis factor (TNF) and interleukin-1 (IL-1) all play a role in triggering this response.

6b.

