Control group: healthy patients 39 healthy controls

PCO:

Population: Oral Lichen Planus patients.

Control: Healthy patients.

Outcomes: Salivary and serum leptin levels.

8. Settings

All patients will be selected from the "out-patient clinic" of Oral Medicine – Oral Diagnosis and Periodontology Department; Faculty of Dentistry, Cairo University.

All controls will be selected from the "out-patient clinic" of any clinical department other than Oral Medicine; Faculty of Dentistry, Cairo University.

B) Participants

9. Eligibility criteria and selection methods

Inclusion criteria:

- Ages for both sexes fall between 30 and 70.
- Symptomatic OLP has been diagnosed clinically and verified histologically.
- Participants who sign a written consent form after being fully informed about the study

Exclusion criteria:

- Treatment with a systemic or locally administered systemic medication within the previous three months before the commencement of the research.

- Patients now taking or who have just stopped taking an NSAID (both steroid and non-steroidal) for pain or inflammation.
- Patients who have been diagnosed with a malignant tumor or tumors.
- Women who are expecting or nursing.
- Inmates, the mentally ill, the elderly, etc., all fall into this category.

rationale for choosing cases and controls for case control studies

All patients will undergo a thorough history and physical examination, and an incisional biopsy of the oral lesion will be taken for histological analysis to confirm a diagnosis of Oral Lichen Planus.

In order to make a fair comparison of salivary and serum leptin levels between cases and controls, we will select individuals who do not have any systemic or oral lesions.

10. Matching criteria and allocation ratio

Matching will be according to Age and Gender

The ratio between cases to controls is 1:1

C) Variables

11. Details about variables

Outcomes: Salivary and serum leptin levels.

Potential confounders: Age and Gender, Type of OLP

Diagnostic criteria: presence of Oral Lichen Planus form(s) (Reticular, Atrophic or Bullous-Erosive forms)

12. Data sources and management

Salivary and serum leptin levels Measurement.

-For patients in Group I, we will collect a saliva sample. Saliva and serum samples from participants in Group II (healthy controls) will be frozen at -80 degrees Celsius until ELISA testing can be performed.

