-Saliva will be collected from each individual after a brief water rinsing and placed on ice in a Falcon tube of the 50 ml capacity. It will take about 5-10 minutes to gather 400 l of unstimulated entire saliva.

- Centrifugation removes insoluble components (bacteria, cellular debris, and glycoprotein aggregates) from a saliva specimen that was snap frozen and packaged in ice or liquid nitrogen immediately after collection.

-Phlebotomists should collect blood samples to ensure participants are comfortable and the sample is of sufficient quality and quantity. Clear spoken and/or written instructions, including information regarding fasting and medication avoidance as appropriate for the intended analyses, should be provided to the study participants. The gold standard for blood donations.

- Under strict hygienic conditions, a venous blood sample of 6 mL is taken from the patient after a fast of 12 hours in a plain red-capped evacuated blood collection tube. Within an hour of sample collection, they will be analysed. After the blood has coagulate, it will be centrifuged at 2000 rpm for 10 minutes to separate the serum. On the same day, regular tests will be performed, and the remaining serum will be frozen at -200 degrees Celsius for serum leptin quantification at a later date.

-The Leptin concentration in the blood will be measured using a commercially available enzyme immunoassay (ELISA) kit from DRG.

-To facilitate data collection and sample identification, we will assign a unique identifier (ID) number to each participant. The main investigator will record all participant information on a standard Excel spreadsheet. The superiors will conduct a secondary inspection.

13. Addressing potential sources of bias

Random selection of cases and controls, all personal and clinical data will be confidential, exposed only on request

D) Study size:

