A power analysis was created to have enough strength to use a two-sided statistical test of the null hypothesis that there is no difference between tested groups regarding salivary and serum leptin levels. By adopting an alpha (α) level of 0.05 (5%), a beta (β) level of 0.2 (i.e. power=80%), and an effect size (d) of (0.736) calculated based on the results of a previous study.¹; the predicted total sample size (n) was found to be (62) cases (i.e. 31 cases per groups). Sample size was increased by (25%) to compensate for possible drop-out during different follow up intervals to be a total of (78) cases (i.e. 39 cases per group). Sample size calculation was performed using G*Power version 3.1.9.7²

14. Study size

Cases: 39... patients

Controls: 39.... Subjects,

E) Quantitative variables

15. Handling of quantitative variables in the analysis

Variables: Oral Lichen Planus disease, types and duration

Potential confounders: Age and Gender, personal habits

Patients will be grouped according to the disease and Outcomes. Potential confounders will be taken into consideration.

F) Statistical methods

16. Statistical methods

Categorical data will be analysed using the chi square test and given as frequency (n) and percentage (%). By examining the distribution of the data, computing the mean and median values, and applying the Kolmogorov-Smirnov and Shapiro-Wilk tests, numerical data will be examined for normality. If the data were found to be normal, the mean and standard deviation values would be reported, and an independent t-test would be used to compare the groups. The data will be given as median and range values if the assumption of normality is broken, and the Mann-Whitney U test and Friedman's test will be used to compare the groups. For all tests, the significance threshold will be set at P 0.05. With IBM® SPSS® Statistics Version 25 for Windows, statistical analysis will be carried out.

IV. Ethics and dissemination:

17a. Research ethics approval

The protocol will be proposed to the ethics committee of faculty of dentistry, Cairo University

17b. Protocol amendments

No amendments are planned; however, if any amendment was formed, it will be published as amendments to the pre-published protocol

17c. Informed consent

All participants in the study will be asked to provide an informed signed consent after full understanding of the study procedure and before allocation in the study.

17d. Confidentiality

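### Collection time and saliva flow are not recorded, so a flow difference between OLP cases and controls could produce or hide a salivary leptin difference and could not be checked afterwards

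*Combined protocol and SAP*

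**What the plan says.** Section 12 (Data sources and management) gives one saliva procedure for all participants: "Saliva will be collected from each individual after a brief water rinsing and placed on ice in a Falcon tube of the 50 ml capacity". The same section then states the amount and the expected duration: "It will take about 5-10 minutes to gather 400 l of unstimulated entire saliva". The unit symbol was probably lost when the text was read from PDF. I take it as microlitres and do not count it as an error. No start time, stop time, weight or flow is mentioned.

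Section 11 defines the outcomes as "Outcomes: Salivary and serum leptin levels". The samples go to ELISA, and no output-per-minute or normalisation step is described. The salivary level is therefore, by inference, a concentration.

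Flow is not among the confounders in Section 11 ("Potential confounders: Age and Gender, Type of OLP") or Section 15 ("Potential confounders: Age and Gender, personal habits"). Section 10 matches on age and gender only. Section 13, on bias, mentions random selection and confidentiality. Section 16 compares the groups with an independent t-test or, if normality fails, with rank tests, and names no covariate.

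The research question in Section 1 states: "Primary outcome is serum leptin levels". Saliva is therefore not primary, but the statement of originality (Section VI) rests on it.

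**The concern.** A concentration in whole unstimulated saliva can depend both on how much leptin enters the mouth and on how much fluid dilutes it. The cases have symptomatic oral mucosal disease, while the controls are chosen to have no systemic or oral lesions. Equal flow in the two groups is therefore an assumption that the plan neither states nor tests.

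If cases salivate less, the same leptin output could give a higher concentration in cases. If they salivate more, a real excess could be hidden. With no time or flow recorded, neither possibility could be examined at analysis, and the information cannot be recovered later. Section 15 promises to take potential confounders into consideration, but that cannot cover a variable that was never collected.

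What is at stake is the interpretation of the salivary result, which is the part the protocol presents as new.

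**Working it through.** **Inputs from the documents.** Amount 400 (microlitres assumed) and time about 5-10 minutes (Section 12). Group size n = 39 (Sections 7 and 14). Two-sided test at 5% (Section D).

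**Flow implied by the plan.** 400/5 = 80 and 400/10 = 40 microlitres per minute. The plan gives no flow figure of its own to reproduce. This is a two-fold range across individuals.

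**Assumptions, none of them in the documents.** True leptin output per minute is equal in the two groups. Concentrations are log-normal with SD of the natural log s = 0.6, 0.8 or 1.0. Mean flow is R-fold lower in cases. A fraction f of the dilution effect applies (f = 1 means concentration is fully inverse to flow). The test is a t-test on the log scale.

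**Formulas.** Spurious standardised difference d = f × ln(R)/s. Noncentrality = d × √(n/2), with √(39/2) = 4.416. Degrees of freedom 2 × 39 − 2 = 76, critical value 1.992.

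**R = 1.25**, ln(1.25) = 0.223:

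| s | d (f = 1) | noncentrality | P(p<0.05), f = 1 | d (f = 0.5) | P(p<0.05), f = 0.5 |
|---|---|---|---|---|---|
| 0.6 | 0.372 | 1.642 | 37% | 0.186 | 13% |
| 0.8 | 0.279 | 1.232 | 23% | 0.139 | 9% |
| 1.0 | 0.223 | 0.985 | 16% | 0.112 | 8% |

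The nominal rate is 5%.

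**How large could R be on the plan's wording?** Suppose all controls take 5-7.5 minutes and all cases 7.5-10, evenly spread, so the groups do not overlap at all. The mean of ln(time) on an interval a to b is (b ln b − a ln a)/(b − a) − 1. This gives 1.826 for controls and 2.166 for cases. The difference is 0.340, and exp(0.340) = 1.40. Even complete separation thus gives a 1.40-fold ratio, not a two-fold one. I therefore use 1.25 for illustration and put no weight on larger ratios.

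**Noise within groups.** If times are uniform over 5-10 minutes, the variance of ln(time) is 0.039. Against assumed log variances of 0.36 (0.6²) to 1.0, that is 0.039/0.36 = 11% down to 4%, a minor matter.

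**A possible safeguard, tested.** One could claim a salivary difference only if concentration differs significantly and concentration × flow points the same way. I simulated this with equal true output, 39 per group, log-flow SD 0.2 and total SD 0.6/0.8/1.0. At R = 1.25 the false-claim rate goes from 37/23/17% to 36/23/17%, so it is practically unchanged. At R = 2, an extreme stress case, it stays near 50%. When output is truly equal, its observed sign agrees by chance about half the time or more.

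**The case against.** The strongest objection is that the bias needs two things the documents do not show: a flow difference between OLP patients and controls, and a salivary leptin concentration that falls as flow rises. That stands. The percentages above are conditional illustrations, and halving the dilution effect brings them close to the nominal rate.

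The plan also has partial protection. It matches on age and gender, requires controls without systemic or oral lesions, applies one collection procedure to everyone, and excludes "Treatment with a systemic or locally administered systemic medication within the previous three months before the commencement of the research". These can limit age-, sex- and drug-related flow differences. They do not address a difference due to OLP itself.

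The research question asks whether levels differ, and a concentration comparison answers that descriptively. This stands too. Flow matters for what a difference means.

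A reader might infer three stronger things, none of which the documents support:

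- That 5-10 minutes implies up to a two-fold flow difference between the groups. It is an approximate duration for individuals in either group, not a range of group means.
- That collecting a set volume is itself the flaw. With the time recorded, a set volume yields flow directly. The gap is the unrecorded time.
- That the study's main result is compromised. Serum leptin is primary and does not depend on saliva flow.

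**Conclusion.** The concern holds in a limited form. As written, the plan could not detect a flow difference between cases and controls, or separate it from a salivary leptin difference. Its size and direction are unknown. Assuming equal output, full dilution, log-scale SD 0.6 to 1.0 and 39 per group, a 1.25-fold lower flow in cases would give a significant result in 16% to 37% of studies, and in 8% to 13% at half dilution. Higher flow in cases would act the other way and could mask a true increase. Only the salivary outcome is affected. Nothing here shows that the salivary comparison will be biased, only that the plan collects nothing with which to find out.

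**What to change.** In Section 12, record start time, stop time and collected volume (or tube weight) for every saliva sample, in the same way in cases and controls.

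In Section 16, report flow rate by group and keep the planned comparison of salivary concentration. Add a supportive comparison of leptin output (concentration × flow), with its estimate and confidence interval. State in advance that if flow differs between groups and the output comparison does not support a difference, the salivary result will be described as a concentration difference that may reflect flow. Do not rely on agreement in direction between concentration and output, since that barely lowers the false-claim rate at R = 1.25.

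The cost is a stopwatch reading, one or two spreadsheet columns and one extra analysis, with no additional visit or sample. The drawback is that if concentration does not in fact depend on flow, multiplying by flow introduces a flow artefact into output. That is why output should stay supportive and not replace concentration.

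### Saliva is not checked for blood or exudate, which is likelier in cases than in controls, so the salivary leptin comparison could be biased by an amount the plan cannot show

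*Combined protocol and SAP*

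**What the plan says.** **Specimen.** Section 12 uses unstimulated whole saliva gathered over roughly 5 to 10 minutes. On preparation it says: "Saliva will be collected from each individual after a brief water rinsing and placed on ice". On clean-up it says: "Centrifugation removes insoluble components (bacteria, cellular debris, and glycoprotein aggregates) from a saliva specimen". It gives no visual check, rejection rule or contamination marker for saliva. Its remark about adequate sample quality concerns blood drawing.

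**Cases.** Section 9 requires that "Symptomatic OLP has been diagnosed clinically and verified histologically". Section 11 gives the diagnostic criterion as "presence of Oral Lichen Planus form(s) (Reticular, Atrophic or Bullous-Erosive forms", so the bullous-erosive form is eligible. Section 9 adds that "an incisional biopsy of the oral lesion will be taken for histological analysis". The timing of that biopsy relative to saliva collection is not stated.

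**Controls.** They come from the faculty's other dental outpatient clinics. Section 9 says of them: "we will select individuals who do not have any systemic or oral lesions".

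**Bias and analysis.** Section 13 lists only random selection and confidentiality. Section 11 includes type of OLP among the potential confounders. Section 15 lists OLP types among the variables and says confounders will be considered. For leptin, Section 16 specifies group comparisons by t-test or a rank test, with no adjustment and no analysis by OLP form.

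**Place of the outcome.** The research question covers both fluids and names serum leptin as primary. The originality statement rests on saliva.

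**The concern.** Centrifugation, as the protocol describes it, takes out particles. The protocol's introduction calls leptin a polypeptide hormone. Leptin that enters the mouth dissolved in plasma or exudate would therefore pass into the supernatant and be measured as salivary leptin. A rinse beforehand may clear blood already present but does not stop oozing during the collection minutes.

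The possible sources are unevenly spread between the groups. Erosive lesions and the biopsy wound belong to cases, and controls are selected to be free of oral lesions. If leptin is higher in serum than in saliva, leakage would push the case mean upward. A higher salivary value in cases could then reflect serum entering through damaged mucosa, and nothing collected under the plan would help a reader judge how much. This matters because saliva carries the study's claim to novelty. Visible blood also has to be noted at collection, since it cannot be reconstructed from a stored supernatant.

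**Working it through.** **Inputs from the protocol.** 39 cases and 39 controls, two-sided test at 0.05 (study size section). The protocol gives no figure for contamination, so there is none to reproduce on this point. The 39 per group does follow from its own steps: 62 × 1.25 = 77.5, rounded to 78, or 39 per group.

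**Inputs the protocol does not give (assumed).** The serum-to-saliva leptin ratio R, the fraction f of a contaminated specimen that is serum, the share q of cases contaminated, and the coefficient of variation (CV) of salivary leptin.

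**Step 1: one contaminated specimen.** With uncontaminated salivary leptin set to 1, the measured value is (1-f) × 1 + f × R, so the relative change is f(R-1).

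| f | R = 10 | R = 100 |
|---|---|---|
| 0.1% | 0.001 × 9 = 0.9% | 0.001 × 99 = 9.9% |
| 1% | 0.01 × 9 = 9% | 0.01 × 99 = 99% |

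At R = 1 leakage adds nothing. Below R = 1 the change is negative and never larger in size than f itself. Upward bias therefore depends on serum leptin exceeding salivary leptin.

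**Step 2: the group comparison.** The table applies to a contaminated specimen, not to the case mean. If a share q of cases is contaminated with relative rise r, controls are not, and the SD is CV × mean in both groups, the bias is q × r / CV in SD units. With q = 0.5 and CV = 1.0:

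- r = 10%: 0.5 × 0.10 / 1.0 = 0.05 SD
- r = 50%: 0.5 × 0.50 / 1.0 = 0.25 SD
- r = 100%: 0.5 × 1.00 / 1.0 = 0.50 SD

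**Step 3: the consequence for the test.** With no true difference, 39 per group and a two-sided t-test at 0.05 (noncentral t), the chance of a significant salivary result is:

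| Bias (SD) | Chance of significance |
|---|---|
| 0 | 5% |
| 0.05 | about 5.5% |
| 0.1 | about 7% |
| 0.2 | about 14% |
| 0.25 | about 19% |
| 0.3 | about 26% |
| 0.5 | about 59% |

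Under these assumptions, a rise of about 10% in half the cases hardly matters, while a doubling in half the cases would often produce a false finding.

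**Step 4: can the planned analysis handle it?** Section 11 treats type of OLP as a confounder, but controls have no OLP type, so it cannot be entered as an ordinary covariate in a case-control comparison. A restricted comparison, such as non-erosive cases against controls, is possible. Section 16 does not specify one.

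**The case against.** The strongest case against the point is that direction and size rest on quantities the protocol does not contain. That stands. The assumed range of 0.9% to 99% per specimen runs from trivial to a doubling, and only its upper end seriously disturbs the group test.

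A reader might infer that leakage can occur only in cases. The documents do not support this. Controls are dental outpatients, and no periodontal or gingival-bleeding criterion is stated for either group, so blood in control saliva is not excluded. The supportable statement is that leakage is more likely in cases.

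A reader might also infer that the plan overlooks lesion form. It does not: Sections 11 and 15 name it. What is missing is an analysis that uses it.

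It is also fair to say that the research question asks only whether levels differ, and the originality statement claims only a first measurement. Neither claims local production of leptin. Leakage through a lesion is arguably a consequence of the disease, so it bears more on what a difference means than on whether one was measured. That holds for leakage from lesions. It holds less well for bleeding from a biopsy wound, which is a study procedure.

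Finally, the remedies are imperfect. Looking for red colour misses clear exudate. Dropping tinged specimens may remove erosive cases selectively. Non-erosive cases may also have a fresh biopsy wound. These points limit what the checks can prove, but they do not make the checks worthless.

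**Conclusion.** The point holds as a possible, unmeasured bias in the salivary comparison. The documents show whole saliva, clean-up aimed at insoluble material, likelier leakage in cases, no contamination check, and no specified analysis by OLP form. They do not show that leakage occurs, that it raises leptin, or by how much. An upward bias requires R above 1, and its size depends on f, R, the share of cases affected and the salivary CV, all of which are assumed here.

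It would be tempting to let a salivary claim stand only if the difference persists in non-erosive cases. That rule is not supported. A smaller difference there could equally reflect a true gradient by lesion form, and the protocol itself states an interest in leptin and disease severity. The subgroup is also small: with an assumed 19 non-erosive cases against 39 controls, power at the protocol's d = 0.736 is about 73%, and with 13 it is about 62%.

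The serum primary outcome and the sample size are unaffected. The change is worth making because it is cheap and because the salivary result carries the novelty of the study.

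**What to change.** **Section 12.** Inspect every saliva specimen before centrifugation, in both groups and by the same rule. Record any visible blood tinge and recollect where possible. State whether saliva is collected before or after the biopsy.

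**Section 16.** Keep the planned salivary comparison and add two sensitivity comparisons of salivary leptin:

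- (a) excluding visibly blood-tinged specimens in both groups;
- (b) non-erosive cases against controls, using the OLP form already listed as a variable.

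Report both as estimates with confidence intervals. Use them to qualify the interpretation, not as a condition for claiming a difference.

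**Cost.** A look at each tube, one recorded field, and two further comparisons. A few specimens may be lost, and precision is lower in the sensitivity analyses. Clear exudate will still be missed, and attenuation in (b) would have more than one explanation, so the report should say both.

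### The design matches on age and gender and the plan promises to consider confounders, but Section 16 offers only unpaired, unadjusted tests, plus a Friedman test with no blocks to work on

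*Combined protocol and SAP*

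**What the plan says.** All references are to the combined protocol and SAP.

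- **Section 10 (matching):** "Matching will be according to Age and Gender" and "The ratio between cases to controls is 1:1". It does not say whether matching is by individual pair or by frequency.
- **Section 11 (variables):** lists age, gender and type of OLP as potential confounders.
- **Section 15 (quantitative variables):** gives a different list, "Potential confounders: Age and Gender, personal habits", and promises that "Potential confounders will be taken into consideration". Type of disease appears here as a study variable: "Variables: Oral Lichen Planus disease, types and duration". The habits are not named.
- **Section 16 (statistical methods):** "Categorical data will be analysed using the chi square test". For normal numerical data, "an independent t-test would be used to compare the groups". Otherwise, "the Mann-Whitney U test and Friedman's test will be used to compare the groups". No regression, ANCOVA, stratified analysis, paired test or covariate list appears.
- **Research question (Section 1):** names serum leptin as the primary outcome; salivary leptin is the other outcome.
- **Background (Section 6b):** says leptin rises with body fat and body mass index. Body mass index is neither a matching factor nor a listed confounder.

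**The concern.** Section 15 makes a commitment that Section 16 gives no means of keeping. In practice the confounders will either be ignored or be adjusted for by choices made after the data are seen.

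Three separate things are at stake.

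1. **Age and gender.** Matching removes their contribution to the difference between group means. The unpaired tests still leave it in the standard error, so the design pays for precision that the analysis does not use.
2. **Friedman's test.** It ranks values within blocks. The plan defines no pairs as blocks and schedules no repeated leptin measurement. It sits beside Mann-Whitney, which assumes independent groups, so the two named tests assume opposite data structures and no rule chooses between them. With two conditions, Friedman's test is in effect a sign test.
3. **Personal habits.** They are neither matched nor adjusted for. The plan names them as possible confounders and then leaves them unhandled.

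**Working it through.** **Inputs from the plan (Sections D and 10):** two-sided alpha 0.05, power 80%, d = 0.736, 31 per group before drop-out and 39 after, ratio 1:1. **Assumed, because the plan gives no figure:** within-pair correlation ρ, and the prevalence and effect of any habit.

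**1. The plan's own sample size.** For an independent t-test the noncentrality is d·√(n/2).
- n = 30: 0.736 × √15 = 2.851, power 80.0%
- n = 31: 0.736 × √15.5 = 2.898, power 81.4%
- n = 39: 0.736 × √19.5 = 3.250, power 89.4%

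The stated 31 per group is therefore one more than the t-test needs, and 62 × 1.25 = 77.5, rounded to 78. The calculation assumes an unpaired, unadjusted comparison, as Section 16 does.

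**2. Effect of matching on the planned tests.** With pairs correlated at ρ, the true variance of the mean difference is (1 − ρ) times what the unpaired test assumes. Its standard error is too large by the factor 1/√(1 − ρ), and the effective critical value rises by the same factor. At n = 39 the nominal critical value is 1.992 (76 df). At ρ = 0.3 it becomes 1.992 × 1.195 = 2.381, whose two-sided t probability is 0.0198; simulation gives 0.0199.

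Paired t-test power uses dz = d/√(2(1 − ρ)). At ρ = 0.3, dz = 0.736/√1.4 = 0.622, noncentrality 0.622 × √39 = 3.88, power 96.6%.

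| 39 per group | ρ = 0 | 0.2 | 0.3 | 0.4 |
|---|---|---|---|---|
| Standard error too large by | 0% | 12% | 20% | 29% |
| True alpha, independent t | 5.0% | 3.0% | 2.0% | 1.2% |
| True alpha, Mann-Whitney | 5.1% | 2.9% | 2.1% | 1.4% |
| Power, independent t | 89% | 92% | 93% | 94% |
| Power, Mann-Whitney | 88% | 90% | 92% | 93% |
| Power, paired t | 89% | 94% | 97% | 98% |
| Power, regression on group, age, sex* | 89% | 95% | 97% | 99% |

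*Age and sex explain 0, 20, 30 and 40% of the variance; sex is matched exactly and age closely. At 31 per group the regression has 81, 89, 93 and 96%, and the independent t-test 81, 84, 85 and 87%. Mann-Whitney, alpha and regression figures are simulated on normal data.

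**3. Habits, illustration only.** Bias = prevalence gap × effect on leptin.
- Low: 0.10 × 0.3 SD = 0.03 SD, and 0.03/0.736 = 4% of d
- High: 0.30 × 0.5 SD = 0.15 SD, and 0.15/0.736 = 20% of d

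At the high end, the false-positive rate of the t-test with 39 per group is 10.0, 7.5, 6.2 and 4.9% at ρ = 0, 0.2, 0.3 and 0.4. At the low end it is about 5, 3, 2 and 1%.

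**4. Power cost of adding habits to the model.** Assumed worst case: each habit has prevalence 50% vs 20% and no effect on leptin, and age and sex explain nothing.

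| Habits in model | 31 per group | 39 per group |
|---|---|---|
| 1 | about 75% | 86% |
| 2 | 70% | 81% |
| 3 | 66% | 77% |

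**The case against.** The strongest reply is that age and gender are already handled by design, so leaving them out of the analysis does no harm to validity. That is right. A reader might infer from the missing adjustment that the primary test yields too many false positives for age and gender, or that the sample size is too small. The documents support neither: under matching the error runs the other way, and the stated sample size reproduces.

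A second reply is that the harm from habits is conjecture. That also stands. The plan does not define the habits, and nothing in it links any habit to leptin. A reader might conclude that habits bias the primary comparison and must all enter the primary model. The first part is possible but not shown. The second would be costly: in the worst case above, three habits bring power below 80% even at the full 39 per group.

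Two further defences are weaker. Random selection (Section 13) does not balance habits between cases from the Oral Medicine clinic and controls from other departments. The chi-square test could reveal a habit imbalance but would not correct it.

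Friedman's test could take matched pairs as blocks, but the plan does not say so or state that pairs exist. The Mann-Whitney test named beside it remains usable, so this is a misapplied method and not a failure of the primary comparison.

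**Conclusion.** The point holds as a mismatch between design and analysis that should be corrected; it does not invalidate the study. If age and gender predict leptin, the planned tests are conservative: true alpha of about 3% to 1% and a standard error 12% to 29% too large at ρ = 0.2 to 0.4 with 39 pairs, with power above 80% throughout. At ρ = 0 there is no loss and no gain.

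These figures assume individual pairs and normal data, and the correlations are assumptions. Under frequency matching the direction is the same, because age and sex are balanced between groups but still inflate the within-group SD.

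Friedman's test has no place in a two-group comparison without defined blocks. Type of OLP exists only in cases, so it cannot confound the case-control contrast. Bias from habits is a possibility the plan itself raises, but the 0.03 to 0.15 SD range is illustrative, and the error rate clearly exceeds 5% only for the larger bias at low correlation.

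**What to change.** - **Section 16:** make the primary analysis of serum leptin a linear regression on group, age and sex, and use the same model for salivary leptin. Fix the scale (for example log) in advance. The model works under individual or frequency matching and keeps a participant whose match is lost. Delete Friedman's test from the two-group comparison.
- **Section 10:** state the matching type. If individual, record a pair ID and add a paired t-test or Wilcoxon signed-rank test as a sensitivity analysis.
- **Sections 11 and 15:** use one confounder list. Remove type of OLP from it and analyse type within cases only. Name the habit of interest.
- **Sensitivity analysis:** prespecify adjustment for at most one named habit, and for body mass index if recorded. Do not put an open list of habits in the primary model.

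**Cost.** Wording, a little more analysis work, and possibly some extra data collection: Section 12 plans a spreadsheet of participant information but does not list habits or body mass index. Power for the age and sex model at zero correlation is about 81% at 31 and 89–90% at 39 per group, essentially that of the t-test. With one unbalanced habit (50% vs 20%) the sensitivity analysis has about 75–78% at 31 and 85–87% at 39. The effect on power of adding body mass index was not calculated.
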